7.2 Study enrollment

The number of clients enrolled at each pharmacy.

Analysis population: Cluster-Randomized Control Trial Client Population

7.3 Pharmacy characteristics

Characteristics of enrolled pharmacies, both overall and by study arm/modification, will be presented.

Analysis population: Enrolled Pharmacies

7.4 Characteristics at enrollment

Tables will show descriptive statistics for characteristics at enrollment for all pharmacy clients and for pharmacy PrEP and pharmacy PEP candidates, with product candidacy determined by providers following HIV risk screening and counseling, with breakdowns by study arm. Similar tables will also be presented separately for those who initiated PrEP and those who initiated PEP to understand differences in demographics among those who initiated these products across the study arms.

Analysis population: Cluster-Randomized Control Trial Client Population

7.5 Outcomes

7.5.1 Primary outcomes

Our analyses of the primary outcomes of PrEP initiation and PrEP continuation by 60 days will

use cluster-level data for all participants enrolled in the cluster-randomized control trial.

7.5.1.1 *Effect of intervention on PrEP initiation at 60 days*

Analysis Population: Cluster-Randomized Control Trial Population

The primary analysis will aim to estimate the effectiveness of the pharmacy-delivered PrEP intervention as measured by the number of PrEP initiations by 60 days at each pharmacy in the cluster-randomized control trial phase of the study.

If data are available from pharmacies that dropped out after a period of time in the study, we will attempt to include these data. We will do so by modifying the offset term (see “Inference” below) to reflect the amount of time the pharmacy participated in the study. For instance, if the study lasts for 16 months and a given pharmacy dropped out after 8 months, the offset for that pharmacy would be half of what it would have been if the pharmacy had completed the study. We will seek to obtain measures of pharmacy volume from all pharmacies, even those that drop out; if obtaining volume measures is not possible for some pharmacies, we will impute these measures using pharmacy-level characteristics.

The primary analysis will include data from all partially completing pharmacies from the time the pharmacy is enrolled to drop out or end of study (intent-to-treat analysis). We will additionally perform a **sensitivity analysis** where dropout pharmacies in which there is evidence of no effort to implement the intervention (e.g., stated lack of interest on the part of the pharmacist, pharmacy provider rarely available and present in the pharmacy to deliver the intervention, failure of pharmacy provider to follow protocol, no participants enrolled, etc.) are excluded; other dropout pharmacies will be included (per-protocol analysis). We will also conduct a **sensitivity analysis** where temporary pauses in implementation (not drop outs) are incorporated by adjusting the denominator.

Descriptive statistics

A table will be produced giving descriptive statistics of number of PrEP initiations by study arm (i.e., 1: client-sustained, 2: implementor-sustained, 3: HTS counselor-supported, 4: SOC referral). To aid in interpretation of the number of PrEP initiations accounting for pharmacy size, we will also present PrEP initiation rates standardized to the median monthly volume among Arm 4 (SOC) pharmacies. The table below shows an example of how the standardization would work for an Arm 1 pharmacy, assuming the median monthly volume among Arm 4 pharmacies is 1000. The formula for the standardized number of initiations is as follows: let n be the observed number of initiations in a pharmacy, and N is that pharmacy’s monthly volume. Let N^* be the median monthly volume in Arm 4. Then the standardized number of initiations, n^* , is

$$n^* = n \times \frac{N^*}{N}.$$

Then n^* is divided by the number of months of implementation for the particular pharmacy to get the standardized rate per month. These estimated rates would be reported by pharmacy (graphically) and averaged by arm (in a table).

Arm 1 Pharmacy: Observed Data	Standardized Data	Reported estimated rate
100 PrEP initiations	50 PrEP initiations	50 initiations/6 months = 8.3 initiations/month
2000 clients/month	1000 clients/month (tied to the median in Arm 4 pharmacies)	

Inference

We will estimate the ratio of PrEP initiation rates (number of initiations per clients served at the pharmacy, accounting for pharmacy volume over the implementation period) comparing each intervention arm to the SOC arm using a Poisson generalized linear model with log link and robust standard errors. The model will allow for overdispersion to account for increased variability in rates. The outcome will be number of self-reported PrEP initiations from the 60-day brief client survey in each pharmacy. A cluster-level analysis was chosen for the outcome of PrEP initiation because the number of individuals enrolling in the study at a given pharmacy was found to be heavily dependent upon the study arm of the pharmacy. Thus, the available denominator for the individual-level PrEP initiation outcome, number of individuals enrolled in the study, was a poor proxy for the quantity of interest, number of pharmacy PrEP candidates (i.e., individuals determined at risk of HIV acquisition who meet the pharmacy PrEP prescribing checklist criteria). Instead, we will pursue a cluster-level analysis where the outcome is number of initiations at each pharmacy and we account for pharmacy volume as a way to make fair comparisons across pharmacies.

The model will include study arm as a four-level categorical (nominal) variable and a continuous offset variable reflecting pharmacy volume (number of clients per unit time). Pharmacy volume will be measured as the number of transactions per month. Estimates of monthly volume will be obtained up to three times in each pharmacy during the course of the study (to account for seasonal variations); missing observations will be imputed, and we will take the average of the three assessments. To account for the stratified randomization procedure, we will adjust for county as a categorical (nominal) variable. As noted in Section 6.7, our missing imputation strategy (i.e., imputing missing outcome data as failures) will not affect the primary analysis of the pharmacy-level count data and will only influence the secondary analysis described in Section 7.5.1.3.

To address potentially large variability in pharmacies, a **sensitivity analysis** will be conducted removing extreme outlier pharmacies to evaluate how the primary results are impacted. To address difference in when participants were reached for follow-up, another **sensitivity analysis** will be conducted that restricts follow-up data to just include those within 30 days (+/-) of their scheduled follow-up visit (the primary analysis will not restrict timing of follow-up data). An additional **sensitivity analysis** will use non-parametric permutation testing to understand the robustness of the findings of the main analysis. To account for possible imbalances across study arms, a common challenge in cluster-randomized trials, we will perform **sensitivity analyses** repeating the analyses with adjustment for pharmacy-level factors considered to be strongly predictive of PrEP initiation and continuation. Finally, a **sensitivity analysis** will be conducted repeating the primary analysis with adjustment for pharmacy-level average time to survey completion to account for delays in survey completion allowing for additional time to engage with PrEP and PEP.

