4.2 Trial

The study is a cRCT in 60 pharmacies. Fifteen pharmacies will be assigned to each of the four study arms: 3 involving pharmacy-delivered PrEP/PEP services (Arms 1-3) and 1 SOC (Arm 4). These pharmacies will have at least 20 months to enroll participants, **Figure 1**, with the option to extend this longer if needed to achieve target sample size.

Figure 1. Overview of study implementation activities over duration of the cRCT.

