4.4 Randomization

4.4.1 Randomization design

Stratified permuted block randomization will be performed to ensure balance by key prognostic covariates in the first stage of the randomization. Specifically, the goal is to achieve balance across the 4 arms by county or county group (4 counties/county groups, each with 15 participating pharmacies plus 5 back-up pharmacies). Randomization will proceed as shown in **Table 1**, which describes the number of pharmacies that will be in each arm by county.

Of note, implementation was originally planned in 2 counties in Western Kenya (e.g., Kisumu and Homa Bay), this was expanded to 2 additional neighboring counties to ensure the pharmacies selected for study participation were spaced far enough away from one another and an ongoing cRCT in the region testing different models of pharmacy-delivered PrEP services for adolescent girls and young women seeking contraception (i.e., to prevent potential contamination).

This randomization strategy results in balance of treatment assignment by county/county group (in each county/county group, 3-4 pharmacies are in each of the 4 arms) and overall (15 pharmacies assigned to each arm). Within each of these stratified blocks, treatment assignment can be permuted. For instance, consider the 20 urban pharmacies in Kiambu County. Three of these will be assigned to Arm 1, 4 will be assigned to each of Arms 2-4, and 5 will be assigned as back-up pharmacies; the arm assignments will be randomized within this block. Note that by pursuing a stratified randomization scheme, analyses must adjust for county/county group (categorical). In addition to determining which arm a given pharmacy is in, it is necessary to determine whether it will be designated as a cRCT pharmacy or a back-up pharmacy.

Table 1: Randomization scheme for the cRCT and back-up distribution.

County	Arm 1	Arm 2	Arm 3	Arm 4	Back-up pool	Total # pharmacies
Kiambu	3	4	4	4	5	15 cRCT + 5 back-up
Nairobi	4	4	3	4	5	15 cRCT + 5 back-up
Kisumu/Siaya	4	3	4	4	5	15 cRCT + 5 back-up
Homa Bay/Migori	4	4	4	3	5	15 cRCT + 5 back-up
TOTAL	15	15	15	15	20	60 cRCT + 20 back-up

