In particular, to estimate power, it was assumed that the average pharmacy flow was the same across the four arms; there is no a priori reason to assume otherwise. We further assumed a coefficient of variation (CV) of 0.25. The coefficient of variation characterizes the variability in number of PrEP initiations (relative to pharmacy size) across pharmacies. While this is difficult to know ahead of time, it is typically <0.25 (Hayes and Bennett, *IJE*, 1999). A CV of 0.25 would roughly correspond to a situation where, for example, the average number of PrEP initiations was 20/pharmacy, and 95% of pharmacies had between 10 and 30 initiations (assuming equal flow across pharmacies); this seems to be a reasonable degree of variability in our setting. Given that the analyses will include comparisons of Arms 1, 2, and 3 vs. 4, we used a Bonferroni correction to our alpha level (two-sided alpha = 0.05/3) for the PrEP 60-day initiation/continuation outcomes and the combined PrEP/PEP outcomes (primary and key secondary outcomes).

Based on the hypothesized number of PrEP/PEP initiations and continuations in **Table 3**, we estimated the power would be very high for comparing Arms 2 and 3 to Arm 4 for PrEP initiation

and continuation (primary outcomes) and the combined PrEP/PEP initiation and continuation outcomes (key secondary outcomes; **Table 4**). For the Arm 1 vs. Arm 4 comparisons, the power is estimated to be 80% for PrEP initiation (as designed), 100% for the combined PrEP/PEP initiation outcome, and lower for the continuation outcomes.

→ **Primary outcome assessment will be completed after a total of 1,119 PrEP initiations are achieved. A study duration of 20 months of implementation is targeted.**

Table 3: Number of PrEP, PEP, and PrEP/PEP initiations and continuations per pharmacy (k=15/arm, k=60 total) for >80% power in our PrEP outcomes of interest

	1: Client-sustained	2: Implementor-sustained	3: HTS supported	4: Referral (SOC)	TOTAL (across 60 pharms)
PrEP initiations	16.13	22.18	26.21	10.08	1,119
PEP initiations	32	48	64	16	2,400
Total PrEP/PEP initiations	48.13	70.18	90.21	26.08	3,519
PrEP continuations	8.06 (50% of initiations)	15.52 (70% of initiations)	20.97 (80% of initiations)	6.05 (60% of initiations)	759
PEP continuations	4.34 (13.6% of initiations)	9.12 (19.0% of initiations)	13.90 (21.7% of initiations)	2.61 (16.3% of initiations)	450

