6.4 Statistical testing and models

Statistical tests will be 2-sided tests and considered statistically significant if $p < 0.05$ (i.e., $\alpha = 0.05$), with the exception of the analyses of the PrEP initiation and continuation outcomes and the combined PrEP/PEP initiation and continuation outcomes, which constitute the primary and key secondary outcomes. These will utilize a significance threshold of $0.05/3 = 0.0167$ to account for the three comparisons of Arms 1, 2, and 3 versus Arm 4.

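### The primary Poisson analysis names no small-sample correction for its robust standard errors; an uncorrected sandwich with a z test would reject about 2 to 3 times too often at the 0.0167 threshold.

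*SAP*

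**What the plan says.** SAP 7.5.1.1 (Inference) estimates ratios of PrEP initiation rates "using a Poisson generalized linear model with log link and robust standard errors". The model has arm (four levels), county (categorical) and an offset for pharmacy volume. A further sentence says that overdispersion will be allowed for, without saying how. 7.5.1.2 applies the same approach, sensitivity analyses included, to PrEP continuation.

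On the number of clusters, 4.2 says "Fifteen pharmacies will be assigned to each of the four study arms", and 4.4.1 adds that "in each county/county group, 3-4 pharmacies are in each of the 4 arms".

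On the threshold for the primary and key secondary outcomes, 6.4 says "These will utilize a significance threshold of $0.05/3 = 0.0167$ to account for the three comparisons". The power calculation in 4.5 uses the same two-sided level.

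On variability, 4.5 says "We further assumed a coefficient of variation (CV) of 0.25". The SAP gives no figure for the spread of pharmacy volumes.

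Among the sensitivity analyses in 7.5.1.1 is one that "will use non-parametric permutation testing to understand the robustness of the findings of the main analysis".

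**The concern.** A sandwich variance is a large-sample device. With about 60 observations and seven coefficients, fitted residuals are smaller than true errors, so the variance estimate is biased low. It is also noisy, and a normal reference ignores that noise. Both effects grow when a volume offset gives a few large pharmacies high leverage, and both hurt more at a cut-off as far in the tail as 0.0167.

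The choice of variance estimator and reference distribution therefore decides whether the Bonferroni threshold gives the protection claimed for it, and whether the intervals for both primary outcomes are wide enough. The SAP leaves that choice to the software default. Arm 1 versus Arm 4 is most exposed, because 4.5 sizes it for only 80% power on PrEP initiation. A very small p-value in Arm 2 or Arm 3 would survive correction.

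**Working it through.** **1. Inputs from the SAP.** Two-sided alpha 0.05/3 = 0.0167 (4.5, 6.4); 15 pharmacies per arm in the Table 1 layout (4.2, 4.4.1); CV 0.25 (4.5); Table 3 means of 16.13, 22.18, 26.21 and 10.08 PrEP initiations per pharmacy in Arms 1 to 4. Parameters: 1 intercept + 3 arm + 3 county = 7.

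**2. Assumed, because the SAP gives no value.** Volume CV of 0, 0.5 and 1.0.

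**3. Reproducing Table 4 first.** With c = 15 clusters per arm:

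power = Φ( √[ (c−1)(m1−m0)² / ((m1+m0) + CV²(m1²+m0²)) ] − z )

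For Arm 1 versus Arm 4, PrEP initiations:
- numerator: 14 × (16.13 − 10.08)² = 14 × 36.60 = 512.4
- denominator: 26.21 + 0.0625 × (260.18 + 101.61) = 26.21 + 22.61 = 48.82
- √(512.4/48.82) = 3.240; z = 2.394; Φ(0.846) = 80.1%

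Table 4 states 80%. The other 11 cells also reproduce, so the planning inputs are read correctly.

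**4. The variance estimators.** With A = Σ μ x x′ and B = Σ (y − μ)² x x′, the uncorrected sandwich (HC0) is A⁻¹BA⁻¹. The n/(n−p) version (HC1) multiplies it by 60/53 = 1.13. HC3 divides each residual by (1 − leverage) before squaring. Average leverage is 7/60 = 0.12, and it is higher for large pharmacies.

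**5. Error under no effect.** Gamma-Poisson counts, mean 10.08 in every arm, CV 0.25, Table 1 layout, arm + county model with log-volume offset. Nominal is 1.67% per comparison.

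| Test | Volume CV 0 | 0.5 | 1.0 |
|---|---|---|---|
| HC0, z: per comparison | 3.3% | 3.8% | 5.0% |
| HC0, z: familywise, all arms null | 8.5% | 10.0% | 12.5% |
| HC1, z: per comparison | 2.4% | 2.8% | 3.9% |
| HC1, t(53): per comparison | 2.0% | 2.5% | 3.6% |
| HC3, t(53): per comparison | 1.3% | 1.5% | 1.6% |
| HC3, t(53): familywise | 3.6% | 4.1% | 4.2% |

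For HC0 with z the multiples of nominal are 3.3/1.67 = 2.0, 3.8/1.67 = 2.3 and 5.0/1.67 = 3.0. Separate runs gave 3.1 to 3.4%, 3.8 to 4.1% and 5.0 to 5.4% in the first row. At the Arm 4 continuation mean of 6.05, HC0 with z gives 3.2%, 3.5% and 4.9%.

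**6. Only Arm 1 null, Arms 2 and 3 at their Table 3 means.** HC0 with z gives 3.1%, 3.5% and 4.6% for Arm 1 versus Arm 4 (1.9, 2.1 and 2.8 times nominal).

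**7. Permutation test stratified by county, all arms null.** 1.6%, 1.7% and 1.7%.

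**8. Power, Arm 1 versus Arm 4, Table 3 means.** HC3 with t(53): 78%, 72%, 61%. HC0 with z: about 87%, 84%, 79%, part of which comes from the inflated error.

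**The case against.** **The SAP does not say that the sandwich is uncorrected.** A reader might infer that the plan commits to an uncorrected estimator and so certainly misses its threshold. It does not: the variant and the reference distribution are left open, and HC3 with t(53) would hold the level at the planning CV. This stands. The defect is a method left unspecified whose ordinary reading is liberal.

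**The overdispersion sentence might cover it.** It does not settle the matter. A common scale factor cancels out of a sandwich variance. If a quasi-Poisson variance was meant in place of the sandwich, then with t(53) error is 0.9, 1.3 and 1.9 times nominal at volume CV 0, 0.5 and 1.0. That is less inflation, but still inflation once volumes differ.

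**Inflation of four times or more.** A reader might expect this. The SAP's inputs do not give it. It takes 3.8 times at a between-pharmacy CV of 0.5 with volume CV 1.0, or 4.4 times with both at 1.0, to come near or pass that mark. The SAP gives neither value, and 4.5 describes CVs as typically below 0.25.

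**All outcomes under 7.5.2.** It is tempting to carry the same figures over to every one of them. Outcomes tested at 0.05 show less inflation (about 1.6, 1.7 and 2.1 times), and PrEP adherence is a score and not a count.

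**A safeguard is already planned.** The permutation test covers both primary outcomes and would expose a liberal Wald result. This stands in part: as a sensitivity analysis it does not set the primary p-value or interval, and the SAP does not say how it permutes.

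**The SAP post-dates unblinding.** Section 7.7 puts unblinding at 6 November 2025 and this version at 16 December 2025. Replacing the primary standard error now would change a pre-specified analysis. This stands and shapes the fix.

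**Conclusion.** The point holds in this form. For both primary outcomes the SAP fixes a tail threshold but not the small-sample method needed to hold it. Under the usual uncorrected sandwich with a z test, error per comparison at CV 0.25 is about 3.3% with equal volumes and about 5% at volume CV 1.0, roughly 2 to 3 times nominal. Familywise error is about 8 to 13%, a figure that assumes all three arms are null. It goes higher only if pharmacies vary more than planned. Simple n/(n−p) scaling reduces the excess without removing it.

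The lower end uses only the SAP's own inputs and equal volumes. The upper end rests on an assumed volume spread. Unequal volumes are plausible: 7.5.1.1 itself anticipates large variability between pharmacies and shortens the offset for those that drop out. None of this shows that any reported result is wrong, since the documents do not say which estimator was used.

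**What to change.** For the primary and key secondary count outcomes tested at 0.0167:

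- **State what was used.** Keep the pre-specified result and name its sandwich variant and reference distribution.
- **Add corrected inference.** Report a bias-corrected sandwich (HC3 or equivalent) with a t reference, labelled post hoc. Set the degrees of freedom as pharmacies analysed minus model parameters. Do not fix them at 53: replacements (4.4.3) and retained dropouts (7.5.1.1) change the number analysed.
- **Report the permutation test beside the primary result.** Permute only the two arms being compared, within county group. Shuffling all four arms tests a global null. In a small run (400 replicates, volume CV 0.5), four-arm shuffling gave 53% power for Arm 1 versus Arm 4 against 74% pairwise, and a size of 0.25% when Arms 2 and 3 were effective.
- **Carry the rule over** to 7.5.1.2 and the combined PrEP/PEP initiation and continuation outcomes.

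The work is some SAP wording and little code. The statistical cost is wider intervals and the lower Arm 1 versus Arm 4 power shown above: about 78% with equal volumes, close to the 80% planned, but 72% and 61% as volumes become more unequal.

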6.7 Missing values

Missing data in the primary outcomes, i.e., PrEP initiation and continuation, are of greatest concern.

The primary analysis of the PrEP outcomes (described more fully below) will rely on data from the brief client surveys to create uniformity between the intervention arms (for which pharmacy dispensing data will also be available) and the SOC arm (for which clinic dispensing data will also be available). To accommodate missing PrEP outcomes, we will impute missing values as failures (i.e., did not initiate or did not continue, depending upon the outcome under consideration). This same strategy will also be applied to our secondary PrEP/PEP outcomes. Note that since the primary analysis relies on pharmacy-level counts of individuals who initiated/continued PrEP/PEP, for the primary analysis, this imputation procedure will be equivalent to a complete case analysis.

In addition to the analyses above, for the analysis of PrEP initiation at 270 days, we will perform a **sensitivity analysis** where PrEP initiation at 60 days is used to impute missing PrEP initiation at 270 days. For instance, if a participant reports initiating PrEP at 60 days, but PrEP initiation status at 270 days is unavailable, we will consider this participant to have initiated PrEP at 270 days. This would be expected to reduce recall bias in the 270 day outcome.

7 Data Analysis

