7.5.1.3 Secondary Analyses

For the outcome of PrEP continuation at 60 days, we will conduct a **secondary analysis** of the proportion of participants continuing PrEP at 60 days among those who initiated PrEP. In particular, we will estimate the risk difference of PrEP continuation between each intervention arm and the SOC arm using a Poisson generalized estimating equations (GEE) model with identity link and robust standard errors (Pedoza and Truong, BMC Med Res Methodology, 2016). The outcome will be self-reported PrEP continuation from the brief client survey. The model will include study arm as a four-level categorical (nominal) variable and adjust for county to account for the stratified randomization procedure. To account for varying cluster size (number of PrEP initiators), we will use an independent working correlation matrix and weights for cluster size (Wang et al., Contemp Clin Trials, 2022). Missingness will be addressed as described in Section 6.7. In the event that this model does not converge or yields invalid estimates (e.g., risk differences or confidence intervals outside of ± 1), we will instead fit a modified Poisson GEE model—i.e., a GEE with log link and robust standard errors (Yelland et al., AJE, 2011)—to estimate the relative risk comparing each intervention arm to the SOC arm. Importantly, as this analysis is restricted to those who have initiated PrEP, randomization is not maintained. Thus, we would need to adjust for factors related to initiation in order to remove the bias incurred by selecting only those who initiate (Hernan and Hernandez-Diaz, Clin Trials, 2012).

Additionally, **secondary analyses** for PrEP initiation and continuation at 60 days will be conducted to evaluate whether the effect of the intervention differs by urban/rural pharmacy status, location in Western vs. Eastern Kenya, or by the proportion of enrolled individuals who (1) are female or (2) over the age of 25. This will be done by adding two terms to the model described in Section 7.5.1.1: the main effect of the subgroup variable (e.g., percent female) and an interaction between the categorical intervention variable and the subgroup variable. As part of this analysis, we will estimate the intervention effects within each subgroup.

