7.7 Post-unblinding update: December 16, 2025

The study team was unblinded to the results of the analysis on November 6, 2025 prior to the final DSMB meeting on November 13, 2025. The last version of this SAP, with all sections finalized with the exception of this post-unblinding update, was on November 5, 2025—prior to unblinding of any study team members. Summary statistics generated for the November DSMB meeting showed notable variability in completion of 60-day surveys across the 4 study arms. To understand the source of this heterogeneity, pharmacy data for the three intervention (i.e., non-SOC) arms were evaluated. These data indicated that a large number of individuals who did not complete the 60-day survey did in fact initiate/continue PrEP/PEP. This indicated that the planned outcome imputation approach, in which individuals who did not respond to the survey were assumed to have failed (i.e., not initiated/continued PrEP/PEP), likely did not reflect the nature of missingness. Following conversations with DSMB members and other experts, the study team decided to change the imputation approach.

The new imputation approach would impute PrEP/PEP outcomes for individuals who did not complete the survey using the proportion of PrEP/PEP initiations/continuations among individuals in the same pharmacy who did respond to the survey. Thus, if Pharmacy A enrolled 100 participants, 70 of whom responded to the survey and 14 of whom (20%) indicated they had initiated PrEP, then the PrEP initiation outcome for the 30 non-responders would be imputed as a binomial random variable with a success probability of 20%. As indicated above, evaluation of the pharmacy record data in the three intervention (i.e., non-SOC) arms indicated that the proportion of individuals who, per pharmacy records, initiated PrEP (for instance) was similar among those who did and did not complete the survey (42.8% and 40.5%, respectively). Thus, while the analysis based on the imputation procedure proposed in Section 6.7 will be reported in the main results manuscript as the pre-specified analysis, emphasis in that paper will be placed on the results from the analysis using the new imputation approach described in this paragraph, noting that this was not prespecified. We note that the decision to shift focus to this new imputation approach was made prior to seeing the results with the new imputation approach.

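### Continuation among PrEP initiators (SAP 7.5.1.3): the source of initiator status is not fixed, the 7.7 imputation does not tie continuation to initiation, and the adjustment called necessary is not specified

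*SAP*

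**What the plan says.** Section 7.5.1.3 plans a secondary analysis of the "proportion of participants continuing PrEP at 60 days among those who initiated PrEP", as a risk difference of each intervention arm against the SOC arm. On data it says: "The outcome will be self-reported PrEP continuation from the brief client survey". On missing data: "Missingness will be addressed as described in Section 6.7".

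Section 6.7 codes a missing outcome as a failure, meaning "did not initiate or did not continue" according to the outcome being analysed. Section 7.5.1.1 adds that this coding leaves the primary pharmacy-level counts unchanged and "will only influence the secondary analysis described in Section 7.5.1.3".

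On the model, 7.5.1.3 says: "The model will include study arm as a four-level categorical (nominal) variable and adjust for county". Later in the same paragraph it notes that restricting to initiators breaks randomization, so that "we would need to adjust for factors related to initiation in order to remove the bias". No factor is named.

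Section 7.7, written after unblinding, reports that survey completion varied notably across arms and that, in the intervention arms' pharmacy data, "a large number of individuals who did not complete the 60-day survey did in fact initiate/continue PrEP/PEP". It therefore imputes each non-responder's outcome by a binomial draw at the proportion seen among responders in the same pharmacy. The worked example covers initiation only.

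**The concern.** Initiation and refill are both items on the brief client survey (section 6.2), so someone who did not complete it lacks both. If initiator status comes from that survey, 6.7 codes this person as a non-initiator, and the person never enters an analysis restricted to initiators. The one analysis that 7.5.1.1 says the rule influences would then be untouched by it as far as whole-survey non-response goes. A responders-only contrast would be reported as failure-imputed.

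Section 7.7 raises a different problem. Section 3 defines continuation as having initiated and then refilled. A continuation draw at the proportion among all responders, made without reference to the initiation draw, gives imputed initiators too low a chance of continuing and lets imputed non-initiators continue. The pull is strongest where response is poorest, so unequal response by arm becomes an apparent arm effect.

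The SAP itself says that the among-initiators contrast is subject to selection bias without further adjustment, yet it does not specify that adjustment. Section 7.5.2 carries the 7.5.1.3 analyses over to other secondary outcomes where appropriate, so the gaps may extend to the 270-day continuation outcomes.

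**Working it through.** **Inputs from the SAP**
- Planned 60-day survey completion 75%, and 80% initiation among completers (section 4.5). These reproduce the enrolment target: 1,119 / (0.75 × 0.80) = 1,865.
- Hypothesized continuation among Arm 4 initiators 60% (Table 3): 6.05 / 10.08 = 0.60.
- Pharmacy A example (7.7): 100 enrolled, 70 responders, 14 initiators; 14 / 70 = 20%.
- Initiation per pharmacy records in Arms 1–3: 42.8% of survey completers and 40.5% of non-completers (7.7).

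The SAP gives no figure for the among-initiators analysis itself, so there is none to reproduce.

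**Assumptions**
- Response of 90% in one arm and 60% in another.
- 8 continuers among Pharmacy A's 14 initiators.
- Responders are representative of their pharmacy.

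**Notation:** q = true share continuing among initiators, r = survey response, p = initiation proportion.

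**Step 1: section 6.7, at q = 0.60 and r = 0.75**
- Initiators by self-report: non-responders leave both numerator and denominator. The estimate is q = 60%, the same as complete case.
- Initiators by records, missing continuation coded as failure: r × q = 0.75 × 0.60 = 45%.

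The two readings differ by 15 points.

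**Step 2: section 7.7 with separate draws**

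Responding initiators continue with probability q. Imputed initiators continue with the proportion among all responders, p × q. The expected share continuing among initiators is therefore q[r + (1 − r)p].

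With q = 0.60 in both arms, so that the true difference is zero:

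| p | r = 0.90 | r = 0.60 | False difference |
|---|---|---|---|
| 20% (Pharmacy A) | 55.2% | 40.8% | 14.4 points |
| 42.8% (7.7, records) | 56.6% | 46.3% | 10.3 points |
| 80% (planning value) | 58.8% | 55.2% | 3.6 points |

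The difference equals q(1 − p)(0.90 − 0.60) = 0.18(1 − p).

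**Step 3: the hypothesized arm values**

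Take 50%, 70%, 80% and 60% continuation in Arms 1 to 4 and p = 0.428, with the assumed 60% response in Arms 1–3 and 90% in Arm 4. The true differences from Arm 4 of −10, +10 and +20 points become −18.0, −2.6 and +5.1. With the response rates reversed, they become +0.9, +19.7 and +29.2.

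**Step 4: coherence in Pharmacy A**

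For the 30 non-responders, separate draws give on average 30 × 0.20 = 6.0 initiators and 30 × 8/70 = 3.4 continuers. Of those continuers, 3.43 × 0.80 = 2.7 were not imputed as initiators. The chance of at least one such person is 1 − (1 − 0.80 × 8/70)^30 = 94%, and a 100,000-run simulation gave the same. Expected continuation among initiators falls from 8/14 = 57.1% to (8 + 6 × 8/70) / 20 = 43.4%.

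**Step 5: sequential draws**

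Drawing continuation only for imputed initiators, at the responders' continuers/initiators ratio, gives q[r + (1 − r)] = q, or 60% whatever the response. The expected number of imputed continuers per non-responder is p × q under both schemes, so expected pharmacy-level counts do not change.

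**The case against.** The strongest reply is that much of this is silence in the SAP, not error.

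- **Source of initiators.** Section 7.5.1.3 does not say that initiators come from the survey, and the Table 5 footnote allows records in other secondary analyses. If records are used, the rule operates and the 7.5.1.1 sentence is right. Even under self-report, the rule acts on a respondent who reports initiating but leaves the refill item blank. This stands: a reader might infer that missing-as-failure can never operate here, and the SAP does not support that. What remains is that self-report is the natural reading. Section 7.5.1.3 says expressly when records replace the survey, and 6.7 chose the survey for uniformity across arms.
- **Section 7.7.** It neither states separate draws nor mentions the among-initiators analysis, and imputing a continuer who did not initiate would contradict section 3. This also stands. A reader might infer that a false difference has in fact been produced, or that the primary results are biased. The first is conditional, and step 5 rules out the second for this mechanism.
- **Adjustment.** The model sentence does not say that arm and county are the only terms. It is fair to call the further adjustment acknowledged but unspecified, and wrong to say that the SAP rules it out.
- **Size.** The 20% comes from a hypothetical pharmacy. The observed 42.8% is the better lead figure and gives about 10 points, not 14. The response rates by arm are assumed.

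**Conclusion.** The concern holds in a limited form, for a secondary analysis. The source of initiator status is not fixed, and the choice moves the Arm 4 illustration between 60% and 45% at 75% response. On the natural reading, the 7.5.1.1 sentence is wrong for whole-survey non-responders. Section 7.7 does not preserve the link between continuation and initiation. If it is used here with separate draws, the false risk difference is about 10 points at 42.8% initiation, with a range of 4 to 14 points for 80% down to 20%. That rests on 60% true continuation in both arms and on 90% versus 60% response. The SAP reports notable variability in completion but no rates by arm, so the actual size and direction cannot be known from it. The adjustment the SAP calls necessary is neither in the stated model nor named.

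**What to change.** 1. State in 7.5.1.3 where initiator status comes from, use the same kind of source in every arm, and correct the 7.5.1.1 sentence to match. If the source is self-report, label the 6.7 version a responders-only estimate.
2. State whether 7.7 applies to 7.5.1.3. Where it does, draw initiation first, then continuation only for imputed initiators, using the same pharmacy's continuers/initiators proportion among responders. A pharmacy with no responding initiators needs no special rule, because its initiation probability is zero.
3. Name the adjustment covariates and put them in the model. They should be pre-treatment characteristics collected at enrolment in all four arms. Section 7.4 names no variables, and section 6.2 lists age, sex, relationship status and risk behaviours under records kept for Arms 1–3 only, so availability in Arm 4 must be checked. Risk behaviours from the follow-up survey would be post-treatment. Otherwise label the contrast unadjusted and descriptive.
4. Date these changes and label them post hoc, since results are unblinded.

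The cost is SAP wording and minor programming. With covariates the identity-link model may fail more often. The SAP already names a log-link fallback, which gives a relative risk instead of a risk difference.
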